QALYs	Quality Adjusted Life Years
RCT	Randomized Controlled Trial
ROI	Return on Investment
SAE	Serious Adverse Event/Serious Adverse Experience
TB	Toothbrush
TP	Toothpaste
UP	Unanticipated Problem
US	United States

PROTOCOL SUMMARY

Title: Influence of Financial Incentives on Oral Disease Management in Young Children (BEhavioral EConomics for Oral health iNnovation = BEECON)

Précis: Rewards have facilitated positive changes in health-promoting behaviors (e.g. smoking cessation, weight loss, and blood glucose and hypertension management). Behavioral economic interventions, especially with small incentives, can lead to healthy behaviors even after incentives end. The project's overall goal is to assess the efficacy of rewards towards promoting early childhood caries (ECC) preventive health behaviors (toothbrushing performance) for young children of predominantly Latino parents/caregivers in Early Head Start (EHS) and day care center programs. In this trial, eligible consenting parent-child participant dyads, within strata and permuted blocks, will be randomized in equal allocation to one of two groups: 1) Monetary Reward or 2) Delayed Monetary Reward Control. Strata will be based on site and smartphone operating system (iOS or Android). Participants in the Monetary Reward group will be eligible to enter into a weekly drawing to receive incentives (rewards) during the first 6 months of the trial. Children will be followed for 12 months to determine reward effects on toothbrushing, fluoride toothpaste (TP) use, plaque score, and caries screening status. Results will inform researchers and public health practitioners on the longer-term maintenance of behavioral changes and oral health screening status following removal of the rewards.

Objectives:

1. The primary objective of this randomized controlled trial (RCT) is to compare the impact of Monetary Rewards (weekly drawings for those with qualifying toothbrushing sessions) versus Delayed Reward Control through 6 months on ECC preventive behaviors. The primary outcome measure is toothbrushing performance, measured as follows: mean of the number of qualifying half-day toothbrushing episodes per week, through the Month 6 visit. (A Bluetooth-recorded toothbrushing episode qualifies if it lasts at least one minute within one of 14 half-day windows in the week.) . 2. Secondary objectives are: to assess the impact of the Monetary Rewards Intervention versus Delayed Reward Control on toothbrushing performance through 12 months to assess sustainability of the

[figure not shown]
behavior after the drawing incentives cease, through 1 month to assess short-term (immediate) impact on the behavior after the drawing incentives and powered toothbrush use begin (i.e. may include novelty effect of power toothbrushes in all participants), and through 3 months to assess mid-term impact on the behavior after the drawing incentives and powered toothbrush use begin (i.e. after potential novelty effect of power toothbrushes ends in all participants); to estimate the short- and long-term cost effectiveness and return on investment of rewards in improving parent/caregiver behaviors and children's oral health; and to assess potential mediation effects of beliefs (behavioral, normative, and control) on intermediate outcomes (intentions, salience, and habit) and primary outcome (toothbrushing performance). The secondary outcome measures are toothbrushing performance, measured as follows: mean number of qualifying half-day toothbrushing episodes per week, through the Month 12, Month 1, and Month 3 visits and net costs to calculate incremental cost effectiveness ratio.

Population:	The study population will be primarily Hispanic/Latino parent-child (ages 6 months to <48 months) dyads and other high-risk racial/ethnic groups from underserved communities in Los Angeles County (N=488 participants, 244 dyads).
Phase:	II
Number of Sites:	Up to 6 Los Angeles County Early Head Start (EHS) and affiliated day care / preschool centers; the study visits will occur at Los Angeles Venice Family Clinic locations at Simms/Mann, Lou Colen, and Robert Levine centers.
Description of Intervention:	The Monetary Reward intervention is a drawing reward, in which participants are eligible for weekly rewards based on toothbrushing performance.
Study Duration:	(a) 25 months from opening enrollment to completing data collection and (b) 32 months from opening enrollment to final data analyses.
Subject Participation Duration:	Each parent/caregiver-child dyad will complete the trial visits in approximately 12 months. The Delayed Reward Control group participants will have the option to continue for another 6

months (i.e., 18 total months) to earn the same monetary rewards as the intervention group.

Estimated Time to Complete Enrollment: Approximately 14 months.

Schematic of Study Design:

2 INTRODUCTION: BACKGROUND INFORMATION AND SCIENTIFIC RATIONALE

2.1 Background Information

Early childhood caries (ECC) remains the most prevalent chronic childhood disease in the United States (Vargas et al., 1998; Poland & Hale, 2003; CDC, 2001) and poses a serious threat to child welfare, particularly among economically disadvantaged, underserved, and migrant children (Ramos-Gomez et al., 2007; DHF, 2006). National ECC prevalence (any decayed, extracted, or filled primary teeth (deft)) among 2–5 year olds was 23% in 2011–2012 (Dye et al., 2015). Mexican-Americans had double the ECC severity of non-Hispanic Whites (Wiener et al., 2015).

Since dental disease risk increases as a child's teeth erupt (ADA, 2014), brushing with fluoridated toothpaste (TP) (smear for children under 3 years old, pea-sized for those 3–6 years old) for 2 minutes twice daily (Creeth et al., 2009) can help prevent ECC. For 1- to 2-year old children, professional application of fluoride varnish (FV) over 2 years is efficacious (Weintraub et al., 2006; Gansky et al., 2007) and the standard of care for prevention. Powered toothbrushes can provide better plaque removal than manual toothbrushes (Yacoob et al. 2014), but may also have a short-term novelty effect. Research participants using powered toothbrushes may also experience a Hawthorne effect from knowing they are in a research study. Both the novelty and Hawthorne effects have been reported to abate after 12 weeks among college students in a randomized controlled trial (RCT) evaluating plaque levels (McCracken et al. 2000).

Types of Rewards. Incentives are a common component of health promotion programs. Recognizing the important role that incentives can play, NIH has placed the evaluation of incentives on health-related behaviors among its highest priority areas for health economics research (NIH, NOT-OD-16-025, 2015).

Lottery prizes (a type of monetary incentive) have been more successful than non-monetary incentives for encouraging more physical activity (Wing et al., 1996), smoking

cessation, and blood donation (Dey et al., 1999; Goette & Stutzer, 2008), but not for encouraging prenatal visit attendance (Laken & Ager, 1995). Non-monetary incentives (e.g., social recognition, gifts) have effectively boosted immunization (Banerjee et al., 2010; Birkhead et al., 1995; Nexoe et al., 1997; Satterthwaite, 1997) and follow-up cancer screening visits (Marcus et al., 1992; Mayer & Kellogg, 1989), and non-monetary incentives may work as well as material gifts especially if aimed at reducing barriers (e.g., transportation) (Melnikow et al., 1997; Smith et al., 1990).

Large incentives may displace intrinsic motivation for behavior change with the expectation of extrinsic rewards to achieve the same health goals, and consequently remove motivation to adhere to new behaviors once rewards are withdrawn (Gneezy & Rustichini, 2000). Similarly, incentives may alter expectations of interpersonal trust (e.g., between patients and doctors) if exchanges with incentives are viewed as monetary transactions (Heyman & Ariely, 2003).

Incentive form and size to motivate sustained behavior change must reflect contextual factors, including interpersonal relations and reciprocity. Populations place different value on the reward associated with different incentive types (i.e., if the reward is viewed simply as a commercial transaction versus as an added symbolic value of interpersonal trust (vis-à-vis social exchange theory) (Gneezy & Rustichini, 2000; Homans, 1974; Burns, 1973).

Lastly, incentive payout form and size affect program sustainability. While cash transfer programs conditional on children's school and health visit attendance (conditional cash transfers) successfully alleviate poverty and promote social goals, health and nutrition, they have high administrative costs (Handa & Davis, 2006). Moreover, policy makers may prefer in-kind to cash transfers (Das et al., 2005). For the same cost, differently structured incentives may have substantially different effects (Volpp et al., 2009; Haisley et al., 2012). Although some studies have included a cost-effectiveness calculation to evaluate an incentive's added value to preventive health behaviors (Kane et al., 2004), none have done so for oral health.

The project's overall goal is to assess the efficacy of rewards towards promoting ECC preventive health behaviors (toothbrushing adherence) for young children of predominantly Latino parents/caregivers in Early Head Start (EHS) and day care center programs.

2.2 Rationale

[figure not shown]
Numerous factors may contribute to parents/caregivers' inability to provide ADA- or AAP-recommended oral health prevention for their children (i.e., consume fluoridated water, brush with a smear/pea-sized amount of fluoridated TP for 2 minutes twice daily, and attend regular oral health appointments by age one or within six months of first tooth eruption). Minimal oral health knowledge and/or literacy, financial obstacles, and

competing influences, such as daily stress, work, housing priorities, childcare needs, transportation, or geographic location, are a few considerations that may result in failure to follow these oral health recommendations. Further, cultural influences may lead to distrust of fluoride, or believing preventive oral care is unnecessary (Butani et al., 2008).

Prospect Theory and Present Bias

The intervention – weekly drawings based on qualifying toothbrushing sessions – draws on insights from several theories from the field of behavioral economics. The design of the drawing is based on aspects of *prospect theory* (Kahneman & Tversky, 1979). Participants who fail to meet the weekly threshold for earning rewards are informed if they would have won the drawing in order to leverage loss aversion and regret aversion, a sense that a person does not want to give up something that is hers. The drawing also leverages nonlinear probability weighting from prospect theory, in which people have a tendency to overweight small probabilities. The reward design also incorporates the theoretical construct, *present-biased preferences* (also known as present bias or hyperbolic discounting) (Ainslie, 1992; Laibson, 1997). This is the tendency to overweight immediate costs and benefits relative to those in the future. The weekly rewards are a way to provide relatively immediate and frequent feedback, both of which can help counter present bias. Rewards may have additional theoretical benefits: increasing salience of the targeted behavior, offsetting a person's limited attention, and promoting habit formation. The following figure shows where in the decision pathway the intervention is hypothesized to affect the preventive behavior, as well as some of the covariates affecting behavior.

Conceptual model: How incentives can affect toothbrushing

Rewards have facilitated positive changes in health-promoting behaviors, such as quitting smoking (Marteau et al., 2009; Rogers et al., 2014), weight loss (John et al., 2011), and managing blood glucose and blood pressure (Sen et al., 2014). Conditional rewards are particularly effective in encouraging behavioral changes; in some cases small incentives can be equally effective or more effective than larger ones (Marteau et al., 2009; Sen et al., 2014). These “behavioral economic” interventions can lead to healthy behaviors even after incentives end, particularly with smaller incentives (Sen et al., 2014). To date, no study has evaluated such a program for oral health.

2.3 Potential Risks and Benefits

2.3.1 *Potential Risks*

This study poses minimal risk to participants. Study participation is completely voluntary, and participants may discontinue participation at any time without prejudice. Regarding study questionnaires, parent participants may experience psychological discomfort in discussing personal health information or negative experiences at a dental or other relevant office (such as enrolling a child in Medicaid). As with any study, there is the potential for loss of confidentiality. Appropriate precautions will be taken to mitigate this risk. Parents/guardians will be reminded not to change the app profile study ID number to any personal identifying information; if they do it will be transmitted to Philips Sonicare. These include the use of unique study codes for participants and password-protected computers for data storage. Compliance with all Institutional Review Board (IRB) regulations concerning data collection, data storage, and data destruction will be strictly observed. Data will be accessible to research personnel only and will be stored and coded according to guidelines set forth by the UCSF IRB.

The child participant could have potential mechanical trauma to the teeth or gingiva from the powered toothbrush. Parents will be carefully instructed on proper brushing techniques to reduce possible oral discomfort.

Additionally, there is a rare chance of tooth brush head disintegration (bristles falling out), which is a potential choking hazard. The powered toothbrush should always be used with adult supervision, and children should be discouraged from chewing on the brush head.

Even though it is extremely unlikely that a child will get access to and eat the TP, using TP pumps will further reduce the chance of toxicity since the pumps require dexterity that children in the study age range likely lack, and the pumps limit the amount of TP dispensed at any one time. Parents will be advised to keep the TP on a counter and out of the reach of all children in the household.

There is a possibility that a participant may experience an allergic reaction to the TP, FV, and/or plaque disclosing solution; however, the likelihood from TP and FV is extremely rare, while the likelihood from disclosing solution is also rare according to the package insert. Parents/caregivers will be instructed to contact the study's Project Manager in the unlikely event that an allergic reaction to a study product is suspected.

Any adverse reactions will be reported as outlined in Section 9.

All parent/caregiver participants will be asked if they are willing to be contacted again for research purposes. For those who agree, personal identifying information (PII), including contact information, will be requested for subsequent contact and interviewing, creating the risk of a loss of confidentiality of contact information. All participants will be informed of this risk and of steps taken to reduce this possibility.

2.3.2 *Potential Benefits*

Each child participating in this trial, regardless of study group, will have a dental screening and FV applied to his/her teeth as the current standard of care, unless the parent reports that it has been applied within the past month. Each child participant will also receive oral hygiene aids, such as a powered smart toothbrush (TB), brush heads, and fluoride TP pumps. As needed, children with early care or urgent care needs (treatment class 2 or 3 as documented in the ASTDD BSS form) will be provided with referrals for dental visits to providers who agree to take their insurance. In addition, parents/caregivers will be provided Anticipatory Guidance in a standardized video format in English or Spanish; families participating in this study may benefit from the Anticipatory Guidance information.

Overall, participants in the study may benefit from an increased awareness of oral health prevention behaviors.

3 OBJECTIVES

3.1 Study Objectives

3.1.1 *Primary*

The primary objective of this RCT is to compare the impact of Monetary Rewards (weekly drawings for those with qualifying toothbrushing sessions) versus Delayed Reward Control through 6 months in predominantly Latino parents/caregivers to increase ECC preventive behaviors of their children enrolled in or waitlisted for a participating Los Angeles County EHS or affiliated day care center program.

3.1.2 Secondary

The secondary objectives are as follows:

- To assess the impact of the Monetary Rewards Intervention versus Delayed Reward Control on toothbrushing performance:
 - Through 12 months to assess sustainability of the behavior after the drawing incentives cease.
 - Through 1 month to assess short-term (immediate) impact on the behavior after the drawing incentives and powered toothbrush use begin (i.e. may include novelty effect of power toothbrushes in all participants).
 - Through 3 months to assess mid-term impact on the behavior after the drawing incentives and powered toothbrush use begin (i.e. after potential novelty effect of power toothbrushes ends in all participants).
- To estimate the short- and long-term cost effectiveness and return on investment of rewards in improving parent/caregiver behaviors and children's oral health.
- To assess potential mediation effects of beliefs (behavioral, normative, and control) on intermediate outcomes (intentions, salience, and habit) and primary outcome (toothbrushing performance).

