3.2.2 Secondary

Intermediate toothbrushing performance measures are as follows:

- Mean of the number of qualifying half-day toothbrushing episodes per week, through 1 month for short-term effects
- Mean of the number of qualifying half-day toothbrushing episodes per week, through the Month 3 visit for mid-term effects after any novelty effect would be expected to end,
- Mean of the number of qualifying half-day toothbrushing episodes per week, from Month 6 visit to Month 12 visit for longer-term effects

For the outcomes listed above, the minimum qualifying length of time is 1 minute.

Additional secondary oral health measures will be ascertained:

- Debris Index of the Simplified Oral Hygiene Index for Maxillary Incisors (OHI-MIS) to measure plaque on primary maxillary incisor facial (labial) tooth surfaces at Month 6 and Month 12 visits (mean of 4 ordinal scores)
- TP pump weight change (grams) at Month 6 and Month 12 visits
- Binary measure of Association of State and Territorial Dental Directors Basic Screening Survey (ASTDD BSS) untreated caries status ($dt>0$) at Month 6 and Month 12 visits
- Binary measure of ASTDD BSS caries experience status ($dmft>0$) at Month 6 and Month 12 visits; m is missing due to caries only
- Binary measure of ASTDD BSS severe caries ($dmft 4+$) status at Month 6 and Month 12 visits; m is missing due to caries only
- Binary measure of a dental visit in the past 12 months, obtained through EHS ChildPlus database which records annual dental visit and other required health screenings

To assess potential mediation effects of beliefs (behavioral, normative, and control) on intermediate outcomes (intentions, salience, and habit) and primary outcome (toothbrushing performance), the aforementioned primary and secondary outcome measures will be assessed. Behavioral, normative, and control beliefs will be collected via the BRFQ at each study visit (see Section 8.3). Intentions, salience, and habit will be collected with components of the BRFQ (e.g. intentions to brush child's teeth in the next 6 months, preventive habits for one's self and for one's child, age started brushing study child's teeth.).

To estimate the short- and long-term cost effectiveness and return on investment of rewards in improving parent/caregiver behaviors and children's oral health, net costs will be ascertained (as detailed in Section 12.4).

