4 STUDY DESIGN

We will conduct a stratified RCT testing the impact of monetary rewards on ECC preventive behaviors and oral health. Eligible child-parent/caregiver participant dyads will be consented, enrolled, and, following a 2 week run-in, randomized within strata and permuted blocks in equal allocation to one of two groups: 1) Monetary Rewards or 2) Delayed Reward Control. Strata will be based on site and smartphone operating system. The intervention will be offered for 6 months, and children (ages 6 months through <48 months) will be followed for 12 months to determine reward effects on dental visit attendance, toothbrushing, fluoride TP use, OHI-MIS plaque score , and caries screening status. Results will inform researchers and public health practitioners on the longer-term maintenance of behavioral changes and oral health screening status following removal of the rewards.

The study population will be predominantly low income Hispanics/Latinos who are parents/caregivers with children enrolled in, or waitlisted for, one of the participating Los Angeles County EHS or affiliated day care center programs. After enrollment parents/caregivers will use powered toothbrushes for a 2 week run-in to ensure their technology works and they are willing to follow study procedures; after the enrollment visit and run-in, randomization will occur at a separate visit. Participants who are unable to provide data during the run-in period will not be randomized or continue in the study.

Participants in the Monetary Reward group will be eligible to earn one of two incentive amounts every week for the first 6 months of the trial. A participant who meets a low or high threshold will earn entry in that week's drawing for financial incentives (See Section 6.1 for additional details).

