In the Delayed Monetary Reward Control group, participants will not be eligible to receive any performance-based rewards during the first 12 months, but will receive information on their toothbrushing performance. After the 12-month follow-up visit, the Control group participants will have the option to participate in a delayed 6-month open label extension to earn the same monetary rewards the intervention group was eligible to earn until Month 6. This is not a formal part of this trial, but rather a necessary condition of the trial design to assure that all participating parents/caregivers have the chance to earn the same monetary incentives. Control participants who choose the 6-month extension will follow the same procedures (i.e., texting notifications) as the Monetary Reward intervention group from the 12-month follow-up to an 18-month follow-up; they will be randomized into one of two groups which will convey weekly drawing information to participants either weekly or quarterly. At the 18-month follow-up visit, they will be able to collect the earned incentives when the child attends the visit and the returned TP pump is weighed.

After the Month 6 visit through the end of the trial (Month 12), participants will continue to sync their powered toothbrushes and will receive incentives for syncing, but will not be eligible to receive rewards for toothbrushing performance, to assess behavior maintenance after the rewards have ended.

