12.1 Study Hypotheses

Primary Null Hypothesis H0: No difference between intervention and control group participants in mean number of qualifying half-day toothbrushing episodes per week, through Month 6 visit.

[figure not shown]
Primary Alternate Hypothesis HA: Intervention and control group participants differ in mean number of qualifying half-day toothbrushing episodes in per week, through the Month 6 visit.

Secondary hypotheses relate to differences between intervention and control group participants in the secondary outcomes. (See Sections 3.1.2 and 3.2.2.)

Secondary hypotheses also relate to behavioral economic measures mediating the relationship between the intervention and toothbrushing. (See Sections 2.2 & 12.4.)

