12.4 Final Analysis Plan

Intent-to-treat (ITT) analyses standard in incentive based behavioral economics studies will be utilized (e.g. Halpern *et al.* 2015, Patel *et al.* 2016). Generalized linear mixed models (GLMMs) will be used to compare primary and secondary outcomes over time between groups. GLMMs make fewer missing data assumptions than other methods, which assume missing data are missing completely at random. Identity link will be used for numeric (interval) outcomes (e.g., mean number of qualifying half-day toothbrushing episodes per week, through Month 6 visit; mean OHI-MIS plaque score; and TP pump weight change). The group x time interaction will also be assessed; short-term effects will be assessed for 1 month of the intervention, mid-term effects after the novelty effect of powered toothbrushing usually ends for the Month 3 Visit, and long-term effects for the Month 6 Visit (primary outcome), as well as, maintenance of behavior after removing the incentives for the Month 12 Visit. Recent, powerful Precision Medicine methods which do not inflate Type I error will be used to detect heterogeneity of treatment effects by groups of participants based on baseline characteristics (e.g., Lazar *et al.* 2013). Multiple imputation using chained equations (MICE) for arbitrary missingness patterns (Raghunathan *et al.* 2001; van Buuren 2007) will be used for sensitivity analyses. Supplemental analyses will also explore: a) trajectories of mean number of qualifying half-day brushing episodes per week over time; as well as b1) variability in morning brushing times, b2) variability in evening brushing times, and c) variability in weekday versus weekend brushing times associated with mean number of qualifying half-day brushing episodes, OHI-MIS plaque scores, and ASTDD BSS caries screening measures.

To examine potential impact of timing of drawing reward communication time, GLMM analyses as above will be performed comparing the weekly and quarterly drawing result communication arms for primary and secondary outcome data from Month 12 to Month 18.

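### Sustainability after the drawings stop is defined over two incompatible windows, and the one in the Protocol Summary and section 3.1.2 includes the rewarded months

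*Combined protocol and SAP*

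**What the plan says.** The combined protocol and SAP describes the post-reward brushing outcome in several places.

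- **Section 3.1.2 (secondary objectives):** "Through 12 months to assess sustainability of the behavior after the drawing incentives cease".
- **Protocol Summary, Objectives (secondary outcome measures):** "mean number of qualifying half-day toothbrushing episodes per week, through the Month 12, Month 1, and Month 3 visits".
- **Section 3.2.2 (secondary outcome measures):** a weekly mean "from Month 6 visit to Month 12 visit for longer-term effects". This is the only brushing measure in that list that reaches Month 12.
- **Section 6.1:** performance rewards stop at the Month 6 visit while syncing continues, "to assess behavior maintenance after the rewards have ended".
- **Section 12.1:** the secondary hypotheses concern group differences "in the secondary outcomes. (See Sections 3.1.2 and 3.2.2", so they point to both wordings.
- **Section 12.4:** "The group x time interaction will also be assessed", with the last item in its list of effects being "maintenance of behavior after removing the incentives for the Month 12 Visit". It gives no averaging window and no contrast.

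All of this is current text.

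**The concern.** In the Protocol Summary a single preposition governs Month 12, Month 1 and Month 3. The Month 1 and Month 3 means can only run from the start of the intervention, so the Month 12 mean reads the same way and takes in the whole drawing period. Section 3.2.2 leaves that period out.

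Section 4 says the results are meant to inform readers about "longer-term maintenance of behavioral changes and oral health screening status following removal of the rewards". If an analyst follows the summary or objective wording, an effect that disappears when the drawings stop would still appear as a positive 12-month difference and could be reported as sustained. With two definitions in force, the choice between them could also be made after the data are seen.

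This is not type I error inflation. A 12-month average difference would truly exist in that case; it simply does not answer the maintenance question.

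**Working it through.** **Inputs from the documents**
- Section 12.2: 91 per group, difference 2.65 episodes per week, SD 6.0, two-sided alpha 0.05, stated power 84%.
- Section 6.2: rewards run for 24 weeks, described as 6 months.
- Section 7.2: Month 6 visit at business day 130 (130/5 = week 26), Month 12 visit at business day 260 (260/5 = week 52).

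**Assumptions, not in the documents**
- The difference is 2.65 in every rewarded week.
- Each half-year mean has SD 6.0, and the two correlate at ρ between 0.5 and 1.
- The test is a two-group t-test. The planned model is a GLMM, so the significance rates below are only a guide to size.

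**Step 1. Reproduce the plan's figure.** The standard error is 6.0 × √(2/91) = 0.889, so the noncentrality is 2.65/0.889 = 2.98. The noncentral t with 180 degrees of freedom gives power 0.842, matching the stated 84%.

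**Step 2. Rewarded share of the 12-month mean.** With 24 weeks of drawings, p = 24/52 = 0.462. If the rewarded period is taken to the nominal Month 6 visit, p = 26/52 = 0.500.

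**Step 3. What each window shows.** The through-12-months difference is p × (rewarded difference) + (1 − p) × (post-reward difference).

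| True post-reward difference (the section 3.2.2 target) | Through 12 months, 24 of 52 weeks | Through 12 months, 26 of 52 weeks |
|---|---|---|
| 0 | 2.65 × 24/52 = 1.22 | 2.65 × 26/52 = 1.33 |
| 1.325 (half kept) | 1.223 + 1.325 × 28/52 = 1.94 (73% of 2.65) | 1.325 + 1.325 × 26/52 = 1.99 (75% of 2.65) |
| −1.325 (reversal) | 1.223 − 0.713 = 0.51 | 1.325 − 0.663 = 0.66 |
| 2.65 (all kept) | 2.65 | 2.65 |

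The two windows agree only in the last row.

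**Step 4. Chance of a significant through-12-months result when nothing is sustained.** With q = 1 − p, the SD of the 12-month mean is 6.0 × √(p² + q² + 2pqρ).

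| ρ | SD | Power, 24 of 52 (difference 1.223) | Power, 26 of 52 (difference 1.325) |
|---|---|---|---|
| 1 | 6.00 | 0.277 | 0.317 |
| 0.8 | 5.69 | 0.302 | 0.345 |
| 0.5 | 5.20 | 0.351 | 0.402 |

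The section 3.2.2 mean would be significant 5% of the time in the same situation.

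**Step 5. Does section 12.4 settle the window?** Its interaction isolates maintenance only if the Month 12 level is the section 3.2.2 mean, or weekly counts after the drawings end. If the levels are the cumulative means of the Protocol Summary, the Month 12 contrast again contains rewarded weeks. The text does not say which is meant.

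**The case against.** The strongest reply is that this is a summary line lagging behind the body of the protocol. Section 3.1.2 states an objective and a horizon, while outcomes are defined in section 3.2, where the post-reward window is explicit. Section 12.4 uses visit labels as shorthand for the section 3.2 outcomes: its Month 6 label plainly means the primary outcome, so its Month 12 label could mean the section 3.2.2 measure, and it refers to behavior after incentives are removed. It also plans supplemental trajectories of weekly brushing, which would tend to expose an effect that vanishes. Finally, the significance rates rest on assumed SDs and correlations, complete loss of effect, and a test that is not the planned one; at ρ = 0.5 the upper end is 40%, and at ρ = 0.3 it is 45%.

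Much of this stands. Section 3.2.2 is the better definition and fits section 6.1. The rates are illustrative. A post-reward difference could also be recovered from the 6-month and 12-month cumulative means taken together, which is why the criticism is confined to the through-12-months mean as a stand-alone endpoint.

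The conflict remains, however. The Protocol Summary wording is itself an outcome definition, not just a horizon. Section 12.1 sends the reader to both sections, no text gives one precedence, and the trajectories are exploratory and do not define the endpoint. The result in Step 3 needs no SD, correlation or test.

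**Conclusion.** The concern holds. The sustainability outcome has two incompatible definitions in current text, and the one in the Protocol Summary and section 3.1.2 cannot by itself show sustainability, because 46–50% of its weeks are rewarded in one arm only.

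Taking 2.65 as the effect while rewarded, complete loss afterwards still leaves a difference of 1.22–1.33, and a half-kept effect looks like 73–75% retention. The 28–40% chance of a significant result with nothing sustained depends on the assumptions listed above. The contradiction and the direction of the distortion do not depend on them.

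The consequence is limited to this secondary outcome and arises only if the section 3.2.2 window is not used. It should be fixed.

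**What to change.** 1. In the Protocol Summary and section 3.1.2, replace the through-12-months wording for sustainability with the section 3.2.2 window, Month 6 visit to Month 12 visit.
2. In section 12.4, name that window, or the matching post-reward group-by-time contrast, as the maintenance analysis.
3. If a through-Month-12 mean is kept, label it an overall 12-month average and not evidence of sustainability.

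A minor, optional addition is one sentence relating the end of the drawings to the Month 6 visit. The 24 weeks in section 6.2 end at business day 24 × 5 = 120. At the nominal visit (day 130) no rewarded week falls in the window; an overlap is conceivable only if the visit is more than 130 − 120 = 10 business days early, within the ±28 allowed. Section 6.1 already ends performance rewards at that visit, so little turns on this. Any exclusion of drawing weeks should follow the same calendar rule in both arms.

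The cost is wording in three places plus that optional sentence. Section 4 already has brushing start times transmitted, so no new data, visits or participants are needed.
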